9.4.5 QoL (EORTC QLQ-C30 Score and QLQ-PAN26 Score)

The score calculations are described in Appendix B. The total scaled score for each domain in both the Questionnaires will range from 0 to 100. The analyses will be performed using the population and treatment groups as described in Table 1 in Section 4.2.

QLQ-C30:

There are 3 scales/domains described in the QLQ-C30 questionnaire. The global health status/QoL scale, functional scale (Physical functioning, Role functioning, Emotional functioning, Cognitive functioning, Social functioning), and symptom scale/items (Fatigue, Nausea and vomiting, Pain, Dyspnoea, Insomnia, Appetite loss, Constipation, Diarrhoea, Financial difficulties) will be analyzed separately.

• Descriptive statistics will be provided for each scaled score and change from baseline for each visit.

QLQ-PAN-26:

There are several domains described in the QLQ-PAN-26 questionnaire. The score in the Pancreatic pain, Digestive symptoms (Gastrointestinal), Hepatic (Jaundice), Altered bowel habit, Poor body image, Satisfaction with the Health Care and Sexuality (Sexual dissatisfaction) domains will be analyzed.

Similar analyses as QLQ-C30 will be performed.

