#### Resected Pancreatic Cancer Subjects

- Difference between 2 dose cohorts in change from Baseline in stool fat at Week 1
- Stool frequency at Weeks 1, 5, 9, and 13 comparing to Baseline, and the difference in change from Baseline to Week 1 between 2 dose cohorts
- Stool consistency at Weeks 1, 5, 9, and 13 comparing to Baseline, and the difference in change from Baseline to Week 1 between 2 dose cohorts
- EPI symptoms at Weeks 1, 5, 9, and 13 comparing to Baseline, and the difference in change from Baseline to Week 1 between 2 dose cohorts
- Quality of life (QoL) (European Organisation for Research and Treatment of Cancer [EORTC] Quality of Life Questionnaire [QLQ]-C30 and QLQ PAN26) at Weeks 1, 5, 9, and 13 comparing to Baseline, and the difference in change from Baseline to Week 1 between 2 dose cohorts
- Body weight and body mass index (BMI) at Weeks 1, 5, 9, and 13 comparing to Baseline
- Chemotherapy tolerability
- Serum albumin and pre-albumin at Weeks 5, 9 and 13 comparing to Baseline

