1.0 Introduction

This Statistical Analysis Plan (SAP) describes the statistical analyses for CREON or ABT-SLV245 Study M16-142 titled "Creon® (pancrelipase) therapy for subjects with exocrine pancreatic insufficiency (EPI) due to pancreatic cancer: A double-blind, randomized, parallel design with 2 dose cohorts of pancrelipase in resected pancreatic cancer subjects and an open-label single dose cohort in non-resected pancreatic cancer subjects".

Study M16-142 examines the effects of Creon in subjects with resected pancreatic cancer receiving 2 dosing cohorts, and one dosing cohort in non-resected pancreatic cancer subjects.

The SAP will not be updated in case of administrative changes or amendments to the protocol unless the changes impact the analysis.

Unless noted otherwise, all analyses will be performed using SAS Version 9.4 (SAS Institute Inc., Cary, NC 27513) or later under the UNIX operating system.

This SAP includes changes to analyses described in the protocol version 3.0 dated 22 November 2019. Details are outlined in Section 12.0.

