3.2 Secondary Endpoint(s)

Resected Pancreatic Cancer Subjects

- Change from Baseline to Week 1 in average daily stool frequency. The average daily stool frequency is calculated from the last 3 days prior to each of Baseline and Week 1 visit.
- Change from Baseline to Week 1 in stool consistency, based on the proportion of days having watery stool consistency in the last 7 days prior to each of Baseline and Week 1 visit.
- Change from Baseline to Week 1 in the total EPI Symptoms Score.

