3.3 Additional Endpoint(s)

Resected Pancreatic Cancer Subjects

- Average daily stool frequency for 7 days prior to each of Weeks 5, 9 and 13 visits compared to Baseline visit.
- Stool consistency in the 7 days prior to each of Weeks 5, 9 and 13 visits compared to Baseline visit.
- Total EPI Symptom Score at Weeks 5, 9 and 13 visits compared to Baseline visit.
- The scaled total score for each scale/item as described below of Quality of life (QoL) (European Organisation for Research and Treatment of Cancer [EORTC] Quality of Life Questionnaire [QLQ]-C30 and QLQ PAN26) at Weeks 1, 5, 9, and 13 visits compared to Baseline visit.

QLQ-C30:

- Global health status/QoL.
- Functional scales (Physical functioning, Role functioning, Emotional functioning, Cognitive functioning, Social functioning).
- Symptom scales/items (Fatigue, Nausea and vomiting, Pain, Dyspnoea, Insomnia, Appetite loss, Constipation, Diarrhoea, Financial difficulties).

QLQ-PAN26:

- Pancreatic Pain.
- Digestive symptoms (Gastrointestinal).
- Hepatic (Jaundice).
- Altered bowel habit.
- Poor body image.
- Satisfaction with health care.
- Sexuality (Sexual dissatisfaction).
- Body weight and body mass index (BMI) at Weeks 1, 5, 9 and 13 visits compared to Baseline visit.
- Chemotherapy tolerability (as defined in Section 9.4.6).
 - Difference in expected or planned chemotherapy from the last scheduled visit (Yes / No / Not Applicable, no chemotherapy planned) at Week 1, 5, 9 and 13 visits.
 - Proportion of expected or planned chemotherapy due to chemotherapy tolerability.
 - Proportion of different types of changes due to chemotherapy tolerability (entire regimen permanently discontinued / one or multiple agents permanently discontinued / dose held / dose interrupted / dose reduced / change in treatment administration schedule).
 - Diagnosis of changes due to chemotherapy tolerability (Adverse events / Medical history).
- Serum albumin and pre-albumin level at Weeks 1, 5, 9 and 13 compared to Baseline.

Non-Resected Pancreatic Cancer Subjects

- Change in stool fat from Baseline (Day 1) to Week 1 (Day 8).
- Change from Baseline to Week 1, 5, 9 and 13 in average daily stool frequency. The average daily stool frequency is calculated from the last 7 days prior to each of Baseline and Weeks 1, 5, 9, and 13 visits.

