9.4.4 EPI Symptom Score

EPI symptom score for the efficacy analysis will be calculated at each visit as the total score for the responses to all the 12 questions in the EPI Symptoms Questionnaire. The response score will range from 0 to 4 for each question (0 corresponding to None to 4 corresponding to Very Severe). Therefore, the total score will range from 0 to 48.

The analyses will be performed using the population and treatment groups as described in Table 1 in Section 4.2.

- Change in EPI Symptom Score from baseline to Week 1 will be analyzed similarly to the stool frequency analyses using an ANCOVA model including treatment as a fixed effect (resected population only) and Baseline EPI Symptom score as the covariate for both within dose cohort and for comparison between dose cohorts (resected population only).
- Similar analyses will also be provided for the subset of questions (Question 7, 8 and 10) used for dose modification criteria (resected population only).

- Descriptive summary statistics will be provided for change in EPI Symptom score from Baseline to Week 1, 5, 9 and 13 in both the resected and non-resected population.
- Descriptive statistics per day for EPI Symptom score are presented specifying the mean, standard deviation, median, minimum and maximum of stool frequency for 7 days prior to Baseline (Day 1) and Week 1 (Day 8).

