Pain	PA	2	3	9,19
Dyspnoea	DY	1	3	8
Insomnia	SL	1	3	11
Appetite loss	AP	1	3	13
Constipation	СО	1	3	16
Diarrhea	DI	1	3	17
Financial Difficulties	FI	1	3	28

Table 6.Scoring the QLQ-C30

QLQ-PAN-26, the pancreatic cancer module, is designed for patients at all disease stages undergoing surgical resection, palliative surgical intervention, endoscopic palliation or palliative chemotherapy (Fitzsimmons *et al.*, 1999a,b). The module comprises 26 questions hypothesized as 17 scales and single items specifically related to pancreatic disease symptoms, treatment side-effects, and emotional issues. The scores for QLQ-PAN-26 are calculated in the same way as QLQ-C30.

Score after Linear transformation for each scale:

$$S = \left\{\frac{RS - 1}{range}\right\} * 100$$

where, RS is the Raw Score as described above.

A high score will represent a high level of disease symptoms/problems. The QLQ-PAN-26 has been designed so that all items in any scale take the same range of values. Therefore, the range of *RS* equals the range of the item values. All items are scored 1 to 4, giving range = 3.

	Scale	Number of items	Item Range	Item numbers
Pancreatic Pain	РР	4	3	31,33 to 35
Bloating	BO	1	3	32
Gastrointestinal	GA	2	3	36,37
Taste Loss	TL	1	3	38
Indigestion	IN	1	3	39
Flatulence	FL	1	3	40
Weight	WE	1	3	41
Weak Limbs	WL	1	3	42
Dry Mouth	DM	1	3	43
Jaundice	JA	2	3	44,45
Altered Bowel Habit	AB	2	3	46,47
Poor Body Image	PB	2	3	48,49
Side Effects of Treatment	SI	1	3	50
Future Health Concern	FH	1	3	51
Forward Planning limited	FP	1	3	52
Satisfaction with Health Care	SA	2	3	53,54
Sexual dissatisfaction	SX	2	3	55,56

Table 7.Scoring the QLQ-PAN-26

Appendix C. Missing Data Imputation of Quality of Life (QoL) (EORTC QLQ- C30 and QLQ PAN 26

If 50% or less are unanswered for each functioning, assume that the missing items have values equal to the average of those items which are present for that functioning. The missing items are simply ignored when making the calculations. For example, if a functioning (ith functioning with scores Q_{ij} to the jth question) has range 4 and one of the item (I_{i3}) is missing. Then, following the rule, the raw score for that function will be calculated as:

Raw score (*RS*) =
$$(I_{11} + I_{12} + I_{14})/3$$

Functioning Scale Score (S) = $\left\{1 - \frac{RS - 1}{3}\right\} * 100$

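### The SAP plans no between-dose estimate for the protocol's secondary quality-of-life endpoint at Week 1, and it leaves out all ten QLQ-PAN26 single items without giving a reason

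*SAP*

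**What the plan says.** **Protocol.** Section 3.3, matched by the synopsis, gives the quality-of-life endpoint for resected subjects two parts: change over time and a dose contrast. The wording for the second questionnaire runs: "PAN26) at Weeks 1, 5, 9, and 13 comparing to Baseline, and the difference in change from Baseline to Week 1 between 2 dose cohorts". The endpoint covers both questionnaires without limiting them to a subset of scales.

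**SAP endpoint lists.** Section 3.2 keeps three secondary endpoints for resected subjects: stool frequency, stool consistency and, last, "Change from Baseline to Week 1 in the total EPI Symptoms Score". Quality of life appears in Section 3.3 as an additional endpoint, compared with Baseline only.

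**SAP method.** Under QLQ-C30, Section 9.4.5 states: "Descriptive statistics will be provided for each scaled score and change from baseline for each visit". QLQ-PAN26 is to be handled similarly. Table 1 places these summaries in the FAS, by visit, for High Dose, Low Dose and Overall, using the ATG-Dynamic grouping. For the EPI score, by contrast, Section 9.4.4 analyses Week 1 change "using an ANCOVA model including treatment as a fixed effect (resected population only) and Baseline EPI Symptom score as the covariate", both within and between dose cohorts.

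**Record of changes.** SAP Section 1.0 says the SAP alters analyses described in the protocol and adds: "Details are outlined in Section 12.0". Section 12.0 deals only with type I error and multiplicity.

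**QLQ-PAN26 content.** SAP Appendix B states: "The module comprises 26 questions hypothesized as 17 scales and single items". Table 7 gives scoring for all of them. SAP Sections 3.3 and 9.4.5 name seven for analysis.

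**The concern.** Followed as written, the SAP would complete the study without a planned estimate for part of a declared secondary endpoint.

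The visit matters. Low-dose subjects can be escalated from the Week 1 visit onward (Protocol Section 5.7), and resected subjects may not start chemotherapy until after Week 1 (Protocol Section 5.3). At later visits the ATG-Dynamic grouping moves escalated subjects into High Dose. Week 1 is therefore the only post-baseline visit at which quality of life can be compared between the dose groups before any escalation.

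The protocol's own summary of changes justifies reclassifying exploratory endpoints in resected subjects as secondary on the ground that the sample should allow good estimates. Dropping the estimate without comment runs against that reasoning.

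The QLQ-PAN26 subset is a smaller, related matter. The protocol endpoint names the whole instrument and the SAP scores all of it, but only part is listed for reporting.

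**Working it through.** **1. Endpoints to which Protocol Section 3.3 gives a between-dose component at Week 1**

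| Endpoint | Between-dose analysis in the SAP |
|---|---|
| Stool fat | ANCOVA, LS mean difference, 95% CI, P value (9.4.1) |
| Stool frequency | ANCOVA (9.4.2) |
| Stool consistency | Wilcoxon rank-sum test (9.4.3) |
| EPI symptoms | ANCOVA (9.4.4) |
| QLQ-C30 and QLQ-PAN26 | None; descriptive by dose group (9.4.5) |

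Four of five have a planned comparison. The wording of the SAP endpoint lists does not settle the matter, because Section 3.2 also words its three secondary endpoints as change from Baseline without naming the dose contrast. For those three, the contrast appears in the methods sections. For quality of life it appears nowhere.

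**2. What is produced at Week 1.** SAP Section 4.1 defines the dynamic group at Week 1 by the drug dispensed on Day 1. The Week 1 table will therefore show change side by side for the two starting doses, but no difference between them is specified.

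**3. QLQ-PAN26 count (SAP Table 7)**

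- Stated: 26 questions, 17 scales and single items. A recount of the rows gives 17, and the items sum to 26, so the stated figures are reproduced.
- Named for analysis: pancreatic pain (4 items), gastrointestinal (2), jaundice (2), altered bowel habit (2), poor body image (2), satisfaction with health care (2) and sexual dissatisfaction (2). That is 7 scales and 4 + 6 × 2 = 16 items.
- Not named: 17 − 7 = 10 scales and 26 − 16 = 10 items, so every omitted scale is a single item. They are bloating, taste loss, indigestion, flatulence, weight, weak limbs, dry mouth, side effects of treatment, future health concern and forward planning.
- For QLQ-C30, all 15 scales (30 items) are named, including six single items: dyspnoea, insomnia, appetite loss, constipation, diarrhoea and financial difficulties. No general rule against single items is being applied.

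**4. Precision of the missing contrast.** The documents give no SD for any quality-of-life scale, so only SD units are possible. The inputs are 36 per arm randomised and, as a lower figure, 30 per arm (half of the 60 evaluable for stool fat). That Week 1 questionnaires will be available for 30 to 36 per arm is an assumption, as are equal SDs in the two arms. With no covariate gain:

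half-width / SD of change = t(0.975; 2n − 2) × √(2/n)

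- n = 36: 1.994 × 0.2357 = 0.47
- n = 30: 2.002 × 0.2582 = 0.52

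**5. Number of contrasts.** 15 + 17 = 32 scales. If dose had no effect on any of them, the expected number of 95% intervals excluding zero would be 32 × 0.05 = 1.6.

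**The case against.** Several points on the other side have force.

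- A reader might infer that the trial cannot report quality of life by dose at Week 1. The documents do not support that. Change is tabulated for both dose groups, and if the table carries the SAP's usual n, mean and SD, an unadjusted difference and interval could be worked out from it. What is missing is a prespecified contrast.
- The downgrade is not hidden. SAP Section 3.3 shows it openly, the SAP says it changes protocol analyses, and the protocol leaves details of other efficacy analyses to the SAP. The pointer to Section 12.0 fails for changes in general, not for quality of life in particular. That the change is unexplained still stands.
- A reader might infer that the QLQ-PAN26 scales were picked selectively, or that those closest to EPI were removed. The retained seven are exactly the multi-item scales, which is a consistent line. Altered bowel habit and pancreatic pain (which includes abdominal discomfort) are kept, as are QLQ-C30 diarrhoea, constipation, appetite loss, and nausea and vomiting. Bloating and gas also enter the EPI total score, though not as separate results. Indigestion is not an EPI item. What remains is that no reason is given and that QLQ-C30 single items are treated differently.
- Thirty-two contrasts without multiplicity control invite over-reading, and single items take only four values. This limits how the results should be presented; it does not argue against estimating the contrast.
- SAP Section 12.0 says the study is not for registration or labelling. That bears on severity.

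**Conclusion.** The point holds as a mismatch between protocol and SAP. A declared secondary endpoint, the Week 1 between-dose contrast in quality of life, has no planned estimate, interval or test, and the change is neither recorded nor explained where the SAP says changes are outlined. In addition, 10 of 17 QLQ-PAN26 scales, all single items, are scored but not named for analysis, without a stated reason.

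The contrast could be estimated to about ±0.47 to 0.52 SD of the change, assuming 30 to 36 subjects per arm with Week 1 data and equal SDs. Baseline adjustment could narrow this. A reader might want the figure in score points, but that would need a scale SD, and for the adjusted model a baseline correlation, which the documents do not give.

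The weight is moderate. The primary analysis is untouched, and the evidence does not go as far as selective reporting. The sponsor should still correct it, because the data are already collected and the model is already in the SAP.

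**What to change.** In SAP Section 9.4.5, add wording such as:

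> For resected subjects in the FAS, change from Baseline to Week 1 in the QLQ-C30 and QLQ-PAN26 scale scores will be analysed by ANCOVA with Day 1 dose group as a fixed effect and the Baseline score of that scale as covariate. The LS mean difference between dose groups and its 95% CI will be presented as an estimate, without control for multiplicity.

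Then:

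- Add a Week 1 quality-of-life row to Table 1 using ATG-Day 1, as is done for the Week 1 EPI score.
- Extend the QLQ-PAN26 lists in SAP Sections 3.3 and 9.4.5 to all 17 scales, with at least descriptive statistics for the ten single items.
- Either restore quality of life to the secondary endpoints in Section 3.2, or record its demotion, with the reason, as a change from the protocol. Correct the pointer in Section 1.0 so that it leads to an actual list of changes.

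The cost is SAP wording and extra table rows, with no new data and no new model. The drawback is more unadjusted comparisons, up to 32 if every scale is modelled, so the results should be read as estimates with intervals rather than as tests.

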9.4.6 Chemotherapy Tolerability

The following analysis for chemotherapy tolerability will be provided using descriptive statistics for each visit:

- Number and percentage of subjects with change in expected/planned chemotherapy from the last scheduled visit (Yes / No / Not Applicable, no chemotherapy planned)
- For change in expected/planned chemotherapy = yes, the number and percent of subjects that had this change due to chemotherapy tolerability (Yes / No)
- For both change in expected/planned chemotherapy = yes and change in chemotherapy due to tolerability = yes, number and percent of subjects with each type of changes due to chemotherapy tolerability (entire regiment permanently discontinued / one or multiple agents permanently discontinued / dose held / dose interrupted / dose reduced / change in treatment administration schedule)
- For both change in expected/planned chemotherapy = yes and change in chemotherapy due to tolerability=yes, number and percent of subjects with changes due to Adverse events or Medical history.
- The analyses will be performed in both the resected and non-resected population using the population and treatment groups as described in Table 1 in Section 4.2.

9.4.7 BMI, Body Weight

The change from baseline to each visit in body weight, BMI, hip and waist circumference, will be summarized from Baseline (Day 1) to each post baseline visit using descriptive statistics.

The number and percentage of subjects who had more than $10\% (\ge 10\%)$ reduction in their body weight and for subjects who had more than $10\% (\ge 10\%)$ increment in their body weight for each visit will also be summarized.

Body Mass Index (BMI) is calculated as follows at each visit:

BMI $(kg/m^2) =$ Body Weight (kg) / Body Height2 (m^2) :

The analyses will be performed in both the resected and non-resected population using the population and treatment groups as described in Table 1 in Section 4.2.

9.4.8 Serum Albumin, Pre-Albumin

The analyses will be performed in both the resected and non-resected population using the population and treatment groups as described in Table 1 in Section 4.2.

For all the laboratory parameters of serum albumin and pre-albumin, the change from baseline to each of the post baseline visit (Week 5, 9 and 13), and from baseline to the final post-baseline values will be summarized using descriptive statistics.

9.4.9 Exploratory Analysis for Dietary Intake

The fat intake data will be summarized using descriptive statistics including the average fat intake per day (gram/day) by week and by treatment group. The fat intake data for each subject will be included in a listing as well. Similar descriptive summary and listings will also be developed for protein, carbohydrate and calorie intake data.

Additional exploratory analyses may be performed.

9.5 Efficacy Subgroup Analyses

There is no subgroup analysis planned.

10.0 Safety Analyses

10.1 General Considerations

The analyses will be performed in both the resected and non-resected population using the population and treatment groups as described in Table 1 in Section 4.2.

10.2 Adverse Events

Per the study protocol, all AEs (non-serious and serious) reported from the time of study drug administration until 30 days post discontinuation of study drug administration will be collected. In addition, SAEs will be collected from the time the subject signed the study-specific informed consent.

All AEs and SAEs will be coded using the Medical Dictionary for Regulatory Activities (MedDRA) Organ Classes (SOCs) and preferred terms (PTs), Version 21.0 or higher. Specific adverse events will be counted once for each subject for calculating percentages, unless stated otherwise. In addition, if the same adverse event occurs multiple times within a subject, the highest severity and level of relationship to investigational product will be reported.

10.2.1 Treatment-Emergent Adverse Events

Treatment-emergent AEs (TEAE) is defined as AEs that first occur or worsen on or after the first dose of study treatment in until the last study drug treatment. Pancrelipase acts locally in the gastrointestinal tract and is not absorbed in the body thus the effect of the study drug will disappear right after the drug discontinuation. Therefore, the AEs occurring after the study drug treatment period is not considered to be TEAE. Events where the onset date is the same as the study drug start date are assumed to be treatmentemergent. If an incomplete onset date was collected for an AE, the AE will be assumed to be treatment-emergent unless there is evidence that confirms that the AE was not treatment-emergent (e.g., the AE end date was prior to the date of the first dose of study drug).

Three main analyses for TEAE will be provided:

- Incidence rate of TEAE in the first week of study treatment
- Exposure-adjusted incidence rate for TEAE during the entire treatment period
- Incidence rate of TEAE leading to study drug discontinuation

